10.1 Definition of adverse events and reporting requirements

10.1.1 Adverse events

An adverse event (AE) is any untoward medical occurrence (e.g. any unfavorable and unintended sign (including abnormal laboratory findings), symptom or disease) in a subject or clinical investigation subject after providing written informed consent for participation in the study. Therefore, an AE may or may not be temporally or causally associated with the use of a medicinal (investigational) product.

The investigator has the responsibility for managing the safety of individual subject and identifying adverse events.

Novartis qualified medical personnel will be readily available to advise on trial related medical questions or problems.

The occurrence of adverse events must be sought by non-directive questioning of the subject at each visit during the study. Adverse events also may be detected when they are volunteered by the subject during or between visits or through physical examination findings, or other assessments.

Adverse events must be recorded in the appropriate eCRF capturing AEs under the signs, symptoms or diagnosis associated with them, accompanied by the following information (as far as possible) (if the event is serious refer to [Section 10.1.2](#)):

- a) the severity AE grade
 - mild: usually transient in nature and generally not interfering with normal activities
 - moderate: sufficiently discomforting to interfere with normal activities
 - severe: prevents normal activities
- b) its relationship to the study treatment or the ocular injection procedure. If the event is due to lack of efficacy or progression of underlying illness (i.e. progression of the study indication) the assessment of causality will usually be 'Not suspected'. The rationale for this guidance is that the symptoms of a lack of efficacy or progression of underlying illness are not caused by the trial drug, they happen in spite of its administration and/or both lack of efficacy and progression of underlying disease can only be evaluated meaningfully by an analysis of treatment arms, not on a single subject
- c) its duration (start and end dates) or if the event is ongoing, an outcome of not recovered/not resolved must be reported

- d) whether it constitutes a serious adverse event (see [Section 10.1.2](#) for definition of SAE) and which seriousness criteria have been met
- e) action taken with the study treatment. All adverse events must be treated appropriately. Treatment may include one or more of the following:
 - no action taken (e.g. further observation only)
 - (investigational) treatment interrupted/withdrawn
 - concomitant medication or non-drug therapy given
 - patient hospitalized/patient's hospitalization prolonged (see [Section 10.1.2](#) for definition of SAE)
- f) its outcome:
 - not recovered / not resolved;
 - recovered / resolved;
 - recovering / resolving
 - resolved / resolved with sequelae;
 - fatal or unknown
- g) localization (study eye, fellow eye, systemic)

Conditions that were already present at the time of informed consent should be recorded in medical history of the subject.

Adverse events (including lab abnormalities that constitute AEs) should be described using a diagnosis whenever possible, rather than individual underlying signs and symptoms.

Adverse event monitoring should be continued until 30 days (safety follow-up) after the last administration of study treatment (EOT).

Once an adverse event is detected, it must be followed until its resolution or until it is judged to be permanent (e.g. continuing at the end of the study), and assessment must be made at each visit (or more frequently, if necessary) of any changes in severity, the suspected relationship to the interventions required to treat it, and the outcome.

Abnormal laboratory values or test results constitute adverse events only if they fulfill at least one of the following criteria:

- they induce clinical signs or symptoms
- they are considered clinically significant
- they require therapy

Clinically significant abnormal laboratory values or test results must be identified through a review of values outside of normal ranges/clinically notable ranges, significant changes from baseline or the previous visit, or values which are considered to be non-typical in subjects with the underlying disease. Investigators have the responsibility for managing the safety of individual subjects and identifying adverse events.

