
• To evaluate treatment interval prolongation compared to previous treatment• To estimate the proportions of patients maintained at q12w treatment frequency in the two brolucizumab groups• To evaluate the functional outcomes comparing the two brolucizumab groups• To evaluate the anatomical outcomes comparing the two brolucizumab groups• To evaluate the safety and tolerability of brolucizumab	
• Mean treatment interval (overall as well as per study group comparing treatment intervals from baseline to week 52 in the study vs. 24 weeks to baseline prior to enrollment)• Rate of patients (overall and per group) with prolonged interval compared to mean treatment interval in last 24 weeks prior to enrollment• Comparison of proportions of patients maintained at a q12w interval at week 52 between the two arms• Distributions of patients at q8w/q12w intervals from baseline to week 52• Average change in BCVA from baseline to week 52• Proportions of patients with BCVA improvements of ≥ 5, ≥ 10, and ≥ 15 letters from baseline to week 52• Proportions of patients with BCVA ≥ 69 letters at week 52• Mean change in BCVA from baseline to mean of visits at week 16 to week 28• Change from baseline in CST as assessed by SD-OCT per visit up to week 52• Absence of IRF, SRF, and sub-RPE fluid as assessed by SD-OCT per visit up to week 52• Presence of active CNV leakage as assessed by fluorescein angiography at week 52• Incidence of ocular and non-ocular AEs up to week 52

3 Study design

This study is a 52-week randomized, open-label, multi-center, two arm study for pretreated patients with suboptimal anatomically controlled nAMD. Patients who consent will be screened whether they meet all the inclusion and none of the exclusion criteria to evaluate eligibility. After confirmation of eligibility, patients will be randomized in a 1:1 ratio to one of the two treatment arms:

- Brolucizumab 6 mg “**loading arm**”: 3 x 4-weekly initial injections followed by an injection every 12 weeks;
- Brolucizumab 6 mg “**non-loading arm**”: one initial injection followed by an injection every 12 weeks

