4.1 Rationale for study design

This study is designed as a randomized, open-label, multi-center, two-arm parallel study to assess the efficacy and safety of two different brolucizumab 6 mg regimen for pretreated patients with suboptimal anatomically controlled nAMD.

The primary efficacy endpoint based on BCVA was chosen to evaluate the benefits of treatment in terms of functional outcome. Non-inferiority testing was intended originally related to the primary efficacy parameter BCVA change from baseline. However, due to feasibility reasons, purely descriptive analyses will be performed. Historically, the change from baseline in BCVA at a selected time point is considered appropriate as the primary efficacy endpoint in confirmatory nAMD studies, based on the evidence available from existing anti-VEGF treatments in nAMD (e.g. ranibizumab, aflibercept). The BCVA assessment has its own variability and generally in the clinical practice a change of BCVA ≥ 5 letters would be considered as clinically relevant regardless of the underlying disease.

The BCVA will be evaluated as the mean change from baseline to mean of visits at week 40 to 52 due to the fact, that patients will receive injections at different intervals and timepoints. Patients in the loading arm on a q12w treatment interval may receive their last injection at week 44, whereas patient in the non-loading arm on a q12w treatment interval may receive their last injection at week 48. Shifting from q12w to a q8w treatment regime will also lead to differences in treatment schedule. A difference in the time since the last injection between both arms may affect BCVA gain and could introduce a bias on BCVA gain if measured at a single fixed assessment time point. Averaging change in BCVA from baseline at four time points 12 weeks apart will mitigate this potential bias.

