6.7.2 Instruction for prescribing and taking study treatment

There will be two different treatment regimens (see [Figure 6-2](#)) for IVT injections with different timing for brolucizumab “loading” and “non-loading” treatment arms:

- **Brolucizumab 6 mg “loading”:** Treatment with brolucizumab will be initiated with three loading injections every 4 weeks for three consecutive injections (baseline, weeks 4 and 8). From week 8 onwards, patients will be scheduled to receive one injection of brolucizumab 6 mg every 12 weeks.
- **Brolucizumab 6 mg “non-loading”:** Treatment with brolucizumab will be initiated with one single injection (baseline). From baseline onwards, patients will be scheduled to receive one injection of brolucizumab 6 mg every 12 weeks.

For both study arms:

- The assessment of disease activity will be performed 8 and 12 weeks after the previous injection.
- If disease activity is identified by the investigator for the first time at any visit after / from week 8 respectively, patients should stay on a q12w dosing, if the decline in BCVA is clinically non-significant (BCVA loss \leq 4 ETDRS letters) compared to the previous visit.
- If after / from week 8, a BCVA-loss of \geq 5 ETDRS letters appears compared to the previous visit or disease activity is identified for a second time based on the investigator’s judgement of visual and/or anatomic outcomes and signs of disease activity*, patients must be assigned to q8w dosing.
- One attempt of re-extension to q12w will be allowed based on the investigator’s judgement if no disease activity (DA) is detected during the subsequent visit(s).
- If the patient shows significant DA after the re-extension attempt, injection intervals will be fixed to q8w until the end of the study

- *The disease activity decision should be based on the BCVA loss criterium (BCVA loss ≥ 5 ETDRS letters or ≤ 4 ETDRS letters compared to the previous visit) and beyond that on investigator's judgment of visual and/or anatomic outcomes and signs of disease activity (e.g. IRF, SRF, hemorrhage, leakage, visual acuity loss over time etc.).

[figure not shown]

Figure 6-2 Treatment regimen

Evaluation of Disease Activity (DA):

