10.1.3 SAE reporting

To ensure subject safety, every SAE, regardless of causality, occurring after the subject has provided informed consent and until the last study visit or 60 days after the last administration

of study treatment whichever is later must be reported to Novartis safety immediately, without undue delay, but under no circumstances later than within 24 hours of obtaining knowledge of the events. Detailed instructions regarding the submission process and requirements are to be found in the investigator folder provided to each site. Following this study period, SAEs considered by the investigator to be causal related to study treatment should be reported to Novartis safety. Detailed instructions regarding the submission process and requirements are to be found in the investigator folder provided to each site.

All follow-up information for the SAE including information on complications, progression of the initial SAE and recurrent episodes must be reported as follow-up to the original episode immediately, without undue delay, but under no circumstances later than within 24 hours of the investigator receiving the follow-up information. An SAE occurring at a different time interval or otherwise considered completely unrelated to a previously reported one must be reported separately as a new event.

If the SAE is not previously documented in the Investigator's Brochure or Package Insert (new occurrence) and is thought to be related to the study treatment, a Novartis Patient Safety Department associate may urgently require further information from the investigator for health authority reporting. Novartis may need to issue an Investigator Notification (IN) to inform all investigators involved in any study with the same study treatment that this SAE has been reported.

Suspected Unexpected Serious Adverse Reactions (SUSARs) will be collected and reported to the competent authorities and relevant ethics committees in accordance with EU Guidance 2011/C 172/01 or as per national regulatory requirements in participating countries.

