12.5.2 Safety endpoints

The secondary safety objective and endpoint of this study is as follows:

To evaluate the safety and tolerability of brolucizumab

- Incidence of ocular and non-ocular AEs up to week 52

There are no formal safety hypotheses in this study. For all safety analyses, the safety set will be used. All listings and tables will be presented by treatment arm.

Safety endpoints are based on the variables from safety assessments which include:

- Extent of exposure
- Adverse events
- Ophthalmic examinations

- Vital signs

Safety summaries (tables, figures) include only data from the on-treatment period with the exception of baseline data which will also be summarized where appropriate (e.g. change from baseline summaries). In addition, a separate summary for death including on treatment and post treatment deaths will be provided. In particular, summary tables for adverse events (AEs) will summarize only on-treatment events, with a start date during the on-treatment period (treatment-emergent AEs). A separate summary table will be provided for AEs of study eye, fellow eye and non-ocular AEs.

The on-treatment period lasts from the date of first administration of study treatment to 30 days after the last administration of study treatment (EOT) or EOS whichever is the latest.

Adverse events

A treatment-emergent adverse event is defined as any adverse event that develops after initiation of the study treatment or any event already present that worsens following exposure to the study treatment. Only treatment-emergent adverse events will be presented in the summary tables.

All information obtained on adverse events will be displayed by treatment arm and subject.

The number (%) of subjects with treatment emergent adverse events (events started after the first dose of study medication or events present prior to start of treatment but increased in severity based on preferred term) will be summarized in the following ways:

- by treatment, primary system organ class and preferred term.
- by treatment, primary system organ class, preferred term and maximum severity.
- by treatment, standardized MedDRA Query (SMQ) and preferred term.

Separate summaries will be provided for study medication related adverse events, death, serious adverse events, other significant adverse events leading to discontinuation.

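### Protocol 10.1.1 gives two different ends for adverse event collection, and one of them falls before the week 52 safety endpoint for some patients

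*Protocol*

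**What the plan says.** Protocol 10.1.1 contains two instructions on AE follow-up. One concerns how AEs are found: "The occurrence of adverse events must be sought by non-directive questioning of the subject at each visit during the study". Under Protocol section 3, visits are every 4 weeks and the last assessment is at week 52 for all patients. The other sets an end: "Adverse event monitoring should be continued until 30 days (safety follow-up) after the last administration of study treatment (EOT".

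The safety endpoint in Protocol Table 2-1 and 12.5.2 is "Incidence of ocular and non-ocular AEs up to week 52". The AE tables count events that start in the on-treatment period. Protocol 12.5.2 and SAP 2.1.1 both end that period at "30 days after the last administration of study treatment (EOT) or EOS whichever is the latest". Serious AEs have their own rule in Protocol 10.1.3, "until the last study visit or 60 days after the last administration", with the later date applying.

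Protocol 4.1 explains that the arms finish treatment at different weeks: "Patients in the loading arm on a q12w treatment interval may receive their last injection at week 44", whereas a "patient in the non-loading arm on a q12w treatment interval may receive their last injection at week 48".

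SAP 5.1.2 also uses last injection plus 30 days, as the imputed value for a completely missing AE end date and as a cap on end dates with a missing day.

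**The concern.** The analysis window and the serious AE window each have a later-of clause. The general AE rule in 10.1.1 does not. The tables therefore count a period that one sentence of the protocol tells sites they need not monitor. A site following that sentence could stop entering non-serious AEs while another, following the every-visit instruction, carries on.

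Because the cut-off is tied to the last injection, any loss would depend on the injection schedule, and the schedule is what was randomized. Among patients who stay on q12w, it could fall only in the loading arm. Protocol 4.1 recognises time since last injection as a possible source of bias for visual acuity and averages visits to reduce it. The AE rule has no comparable protection. AE incidence is the only listed safety endpoint, and with about 25 patients per arm a few unrecorded events could alter a descriptive comparison.

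**Working it through.** **Inputs.** Loading arm: injections at weeks 0, 4 and 8, then every 12 or 8 weeks. Non-loading arm: week 0, then every 12 or 8 weeks (Protocol 6.7.2). Treatment ends by week 48 (Protocol section 3). Days are counted from baseline as day 0, so week 52 is day 364. Calling baseline day 1 shifts every date by one and leaves the gaps unchanged.

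**Step 1: reproduce the plan's last-injection weeks.**
- Loading q12w: 0, 4, 8, 20, 32, 44. Last injection week 44.
- Non-loading q12w: 0, 12, 24, 36, 48. Last injection week 48.

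Both agree with Protocol 4.1.

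**Step 2: literal gap before week 52.** Gap = max(0, 364 − (7 × last injection week + 30)).

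| Patient | Last injection | 30-day limit | Gap |
|---|---|---|---|
| Loading, q12w | week 44 (day 308) | day 338 | 26 days (26/364 = 7.1%) |
| Non-loading, q12w | week 48 (day 336) | day 366 | 0 |
| Either arm, q8w throughout | week 48 | day 366 | 0 |
| Either arm, interval switched | week 40, 44 or 48 | day 310, 338 or 366 | 54, 26 or 0 days |

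For example, a non-loading patient injected at weeks 0, 12, 20, 28, 36 and 44 has the same 26-day gap as a loading q12w patient. The week 52 visit window is ±21 days (days 343 to 385; Protocol section 8). If the gap is measured to the actual visit, it is 5 to 47 days for loading q12w and 0 to 19 days for non-loading q12w.

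**Step 3: serious AEs.** For loading q12w, day 308 + 60 = day 368, which is past day 364. There is no gap.

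**Step 4: size in the analysed quantity.** The documents give no AE rate, so I assume a constant 1, 2 or 4 AEs per patient-year. I take the worst case: all 25 loading patients stay on q12w and every site stops at the 30-day limit.
- Events in the gap: 25 × rate × 26/365.25 = 1.8, 3.6 or 7.1.
- Protocol 12.5.2 and SAP 2.8.1 count patients with at least one AE, not events. Patients whose first AE falls in the gap: 25 × [exp(−rate × 338/365.25) − exp(−rate × 364/365.25)] = 0.68, 0.52 or 0.15.

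The any-AE count therefore loses less than one patient in 25. Counts for single preferred terms are affected differently, because most patients will not have had that term earlier.

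**Step 5: SAP 5.1.2.** Take a loading q12w patient with an AE starting on day 345 and no end date. The imputed end is day 338, 7 days before the start. The event still counts towards incidence, because SAP 2.1.1 runs to EOS, but its duration would be negative.

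**Step 6: after alignment.** Under the later-of rule the gap is 0 days in both arms for every patient who attends EOS.

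**The case against.** A reader might infer from the 30-day sentence that AE collection really does stop early in the loading arm, that this arm will look safer, and that late ocular inflammation will go unrecorded. The documents do not support this.

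- The every-visit instruction is in the same section and covers loading-arm completers. The 30-day sentence can be read as a minimum, and it does not tell sites to stop asking or recording.
- Slit lamp examination is done at every visit, and Protocol 8.4.3 sends clinically significant post-baseline findings in either eye to the AE page with no end date. SAP 2.8.4.3 tabulates anterior chamber and vitreous cells by visit.
- Protocol 9.1.1 keeps visits and AE collection going for patients who stop treatment early.
- The 30-day sentence labels its anchor EOT, and Protocol section 3 fixes the end-of-treatment visit at week 48 for everyone. Thirty days from that visit is day 366, which leaves no gap in either arm.
- Not all loading patients will stay on q12w. The phase 3 figures quoted in Protocol 1.1, for treatment-naive patients, are 51% and 56%.

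Most of this stands. It shows that the intent was to collect to EOS, and it removes any claim of established or general bias between the arms. It does not remove the contradiction. The every-visit instruction says how AEs are elicited, while the other sentence says how long monitoring lasts and ties EOT to the last administration rather than to the week 48 visit. The planned listing of AEs after the on-treatment period (SAP 2.8.1) does not settle the matter either, since serious AEs alone could fill it.

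**Conclusion.** The point holds as an internal contradiction about when AE collection ends, which carries a risk of uneven recording. The literal gap is 26 days (7%) for loading q12w patients against none for non-loading q12w patients. It is absent for q8w throughout and possible in either arm after a switch. Only non-serious AEs are exposed.

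The figures rest on nominal visit days. The effect on the any-AE count, below one patient per 25, also rests on assumed constant AE rates and on every site applying the 30-day limit. It is therefore close to a worst case. It would be wrong to conclude that the loading arm will look safer. The most that can be said is that it could, if sites followed the 30-day sentence. The content of Table 8-1 is not in the text available, so its AE row could not be checked and might resolve part of the conflict.

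The imputation mismatch in SAP 5.1.2 does not depend on what sites did. It affects durations, not incidence.

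**What to change.** 1. In Protocol 10.1.1, state that all AEs are collected until EOS/week 52 or 30 days after the last injection, whichever is later. This is the rule the sponsor already uses in Protocol 12.5.2 and SAP 2.1.1, and it agrees with the every-visit instruction.
2. In SAP 5.1.2, replace the cap at last injection plus 30 days with the end of the on-treatment period as defined in SAP 2.1.1, and do not allow an imputed end date before the AE start date. SAP 5.1.3 applies the same rule to concomitant medication and would follow.
3. If follow-up has already ended, report the AE cut-off that sites actually applied and the AE observation time by arm.

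The cost is a short protocol amendment with the approvals required by Protocol 14.1, a small change to the SAP text and programs, and a few more AE entries. No visits are added, since patients already attend every 4 weeks to week 52. If follow-up is over, only items 2 and 3 apply and no amendment is needed.

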10.1.2 Serious adverse events

An SAE is defined as any adverse event (appearance of (or worsening of any pre-existing) undesirable sign(s), symptom(s) or medical conditions(s)) which meets any one of the following criteria:

- fatal
- life-threatening

Life-threatening in the context of a SAE refers to a reaction in which the subject was at risk of death at the time of the reaction; it does not refer to a reaction that hypothetically might have caused death if it were more severe (please refer to the ICH-E2D Guidelines).

- results in persistent or significant disability/incapacity
- constitutes a congenital anomaly/birth defect
- requires inpatient hospitalization or prolongation of existing hospitalization, unless hospitalization is for:
 - routine treatment or monitoring of the studied indication, not associated with any deterioration in condition
 - elective or pre-planned treatment for a pre-existing condition that is unrelated to the indication under study and has not worsened since signing the informed consent
 - social reasons and respite care in the absence of any deterioration in the subject's general condition
 - treatment on an emergency outpatient basis for an event not fulfilling any of the definitions of a SAE given above and not resulting in hospital admission
- is medically significant, e.g. defined as an event that jeopardizes the subject or may require medical or surgical intervention to prevent one of the outcomes listed above

Medical and scientific judgment should be exercised in deciding whether other situations should be considered serious reactions, such as important medical events that might not be immediately life threatening or result in death or hospitalization but might jeopardize the subject or might require intervention to prevent one of the other outcomes listed above. Such events should be considered as "medically significant". Examples of such events are intensive treatment in an emergency room or at home for allergic bronchospasm, blood dyscrasias or convulsions that do not result in hospitalization or development of dependency or abuse (please refer to the ICH-E2D Guidelines).

All malignant neoplasms will be assessed as serious under "medically significant" if other seriousness criteria are not met.

Any suspected transmission via a medicinal product of an infectious agent is also considered a serious adverse reaction.

All reports of intentional misuse and abuse of the product are also considered serious adverse event irrespective if a clinical event has occurred.

